Appendix D SOC internationally agreed order

The internationally agreed order (Guideline on summary of product characteristics, December 1999, European commission) for SOC:

1. Infections and infestations
2. Neoplasms benign and malignant (including cysts and polyps)
3. Blood and the lymphatic system disorders
4. Immune system disorders
5. Endocrine disorders
6. Metabolism and nutrition disorders
7. Psychiatric disorders
8. Nervous system disorders
9. Eye disorders
10. Ear and labyrinth disorders
11. Cardiac disorders
12. Vascular disorders
13. Respiratory, thoracic and mediastinal disorders
14. Gastrointestinal disorders
15. Hepato-biliary disorders
16. Skin and subcutaneous tissue disorders
17. Musculoskeletal, connective tissue and bone disorders
18. Renal and urinary disorders
19. Pregnancy, puerperium and perinatal conditions
20. Reproductive system and breast disorders
21. Congenital and familial/genetic disorders
22. General disorders and administration site conditions
23. Investigations
24. Injury and poisoning
25. Surgical and medical procedures
26. Social circumstances

The other terms are sorted by dictionary code order

Appendix E Potentially clinically significant abnormalities criteria for vital signs

Parameter	PCSA	Comments
Vital signs		
SBP	≤95 mmHg and decrease from baseline ≥20mmHg ≥160 mmHg and increase from baseline ≥20 mmHg	To be applied for all positions (including missing) except STANDING.
DBP	≤45 mmHg and decrease from baseline ≥10 mmHg ≥110 mmHg and increase from baseline ≥10 mmHg	To be applied for all positions (including missing) except STANDING.
Weight	≥5% increase from baseline ≥5% decrease from baseline	FDA Feb 2007.

Appendix F Description of primary and sensitivity analyses of PFS

Table 20 - PFS Primary analysis

Situation	Date of progression or censoring	Outcome
No baseline tumor assessments	Date of first treatment administration	Censored
Documented progression according to investigator	Earlier of: - Date of radiological assessment showing new lesion or progression of non-target lesion - Date of last radiological assessment of target lesions (if progression is based on increase in sum of target lesions)	Event
Death without documented progression according to investigator	Date of death	Event
Both documented progression according to investigator and death	Date of progression	Event
No documented progression according to investigator and no death	Date of last valid tumor assessment without evidence of progression	Censored
Symptomatic deterioration reported and no documented progression according to investigator and no death	Ignored	Ignored
Initiation of new anti-cancer treatment	Ignored	Ignored

Table 21 - PFS sensitivity analysis #1 (progression based on investigator's assessment of lesions, and including symptomatic deterioration)

Situation	Date of progression or censoring	Outcome
No baseline tumor assessments	Date of first treatment administration	Censored
Documented Progression (without symptomatic deterioration) according to the investigator	Earlier of: - Date of radiological assessment showing new lesion or progression of non-target lesion - Date of last radiological assessment of target lesions (if progression is based on increase in sum of target lesions)	Event
Death without documented progression and without symptomatic deterioration	Date of death	Event
Symptomatic deterioration reported with no documented progression according to investigator and no death	Date of symptomatic deterioration	Event
Symptomatic deterioration and documented progression according to the investigator regardless of death occurrence	Earlier of the date of symptomatic deterioration and date of progression	Event
Symptomatic deterioration and death with no documented progression according to the investigator	Date of symptomatic deterioration	Event
Documented progression according to the investigator and death with no symptomatic deterioration	Date of progression	Event
No progression according to the investigator, no death, and no symptomatic deterioration	Earlier of the date of last valid tumor assessment without evidence of progression and cut-off date	Censored
New anti-cancer treatment started	Ignored	Ignored

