6.2.2 Determination of end of clinical trial (all patients)

The first cut-off date for the selection of the selected dose corresponds to the date on which all patients treated in Part 1 (whatever the dose) have had at least 4 postbaseline tumor assessments, experienced confirmed objective response, or have discontinued the study for any reason. However, if the futility criteria of 2 responders is either met or not met with certainty for both arms when all patients have had 2 postbaseline tumor assessments, experienced confirmed objective response, or discontinued the study for any reason, the first cut-off date may be done at that time instead. The recruitment will be put on hold at the time of the interim analysis until the decision regarding dose selection and the start of Part 2 has been made. The recruitment will be authorized in Part 2 only when the selected dose is chosen.

The second cut-off date for primary ORR analysis corresponds to the date on which all patients treated in Part 2a and Part 2b have had at least 4 postbaseline tumor assessments, experienced confirmed objective response, or have discontinued the study for any reason. However, if the primary criteria of 7 responders is either met or not met with certainty at the end of the Part 2a in the selected dose when all patients have had 2 postbaseline tumor assessments, experienced confirmed objective response, or discontinued the study for any reason and when all the patients of the Part 2b have had 2 postbaseline tumor assessments, experienced confirmed objective response, or discontinued the study for any reason, the second cut-off date may be done at that time instead.

If a patient continues to benefit from the treatment after the second study cut-off, the patient can continue study treatment until disease progression, unacceptable toxicity, or patient's refusal of further study treatment, and will continue to undergo all assessments as per the study flow chart.

Patients without documented disease progression but not on treatment at the second cut-off date will be followed for any ongoing AEs. In addition, imaging to document disease progression and survival status will be collected (every 6 weeks) for 6 months after the cut-off date.

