2.1.3.2.4 Progression-free survival

Progression-Free Survival (PFS) is defined as the time interval from the date of the first treatment infusion to the first documented date of disease progression or death due to any cause, whichever occurs first.

Rules for sensitivity analysis

PFS endpoint will be determined considering also clinical/non radiological progression as an event. If clinical/non radiological progression is observed in absence of documented radiological progression, the date of progression will be the date of clinical/non radiological progression. If the first progression is based on documented radiological progression and on clinical/non radiological progression, the date of progression will be the earliest of date of documented progression and date of clinical/non radiological progression.

Censoring rules for all PFS analyses:

For these 2 analyses, in the absence of disease progression or death (or clinical/non radiological progression for sensitivity analysis), the PFS will be censored at the date of last evaluable tumor assessment without documented progression. In addition, the patient without any valid post-baseline tumor assessment will be censored for PFS on the day of the first study treatment infusion (Day 1).

The summarized description of these analyses is given in [Appendix F](#).

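### The PFS sensitivity table caps censoring, but not events, at an undefined cut-off date, which contradicts the SAP's single censoring rule and would lower late PFS if post-cut-off data are analysed

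*SAP*

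**What the plan says.** SAP 2.1.3.2.4 defines a primary PFS analysis and a sensitivity analysis that also counts clinical or non-radiological progression as an event. Under the label "Censoring rules for all PFS analyses" it sets one rule for a patient without an event: "the PFS will be censored at the date of last evaluable tumor assessment without documented progression". It then refers to Appendix F for a summary of the analyses.

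Appendix F gives two different rows for that patient:

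- Table 20 (primary): "Date of last valid tumor assessment without evidence of progression".
- Table 21 (sensitivity): "Earlier of the date of last valid tumor assessment without evidence of progression and cut-off date".

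The event rows of Table 21 (documented progression, death, symptomatic deterioration and their combinations) carry no cut-off. The row for a patient with both kinds of progression, for example, reads "Earlier of the date of symptomatic deterioration and date of progression".

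In the SAP text as published, the term cut-off date appears only in that one cell of Table 21. Protocol 6.2.2 defines two cut-offs, one for dose selection and one for the primary ORR analysis, and Table 21 does not say which it means.

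Protocol 6.2.2 and 10.1.7 plan data collection after the second cut-off. Patients still on treatment "will continue to undergo all assessments as per the study flow chart". For patients off treatment without progression, "imaging to document disease progression and survival status will be collected (every 6 weeks) for 6 months after the cut-off date".

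**The concern.** The sensitivity analysis exists to show what happens when symptomatic deterioration counts as progression. For that, it should differ from the primary analysis in the event definition and in nothing else. Table 21 also changes the censoring rule, and on one side only: a progression or death dated after the cut-off remains an event, while a clean scan after the same date adds no follow-up.

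If post-cut-off records are in the dataset, the sensitivity curve could lie below the primary curve with no symptomatic deterioration at all, and a reader would put the gap down to clinical progression. The late part of the curve is exposed, and SAP 2.4.4.2.5 plans 9-month and 12-month rates. Whatever data are used, a programmer cannot follow both 2.1.3.2.4 and Table 21 as written.

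**Working it through.** **Figure to reproduce.** None. The documents give no expected median, event count or power for PFS.

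**Mechanism.** At an event time with d events, let n be the number at risk under Table 20. Let c be the number of those who have passed their own cut-off, never have an event, and have a later clean scan. The Kaplan-Meier factor is 1 − d/n under Table 20 and 1 − d/(n − c) under Table 21. The second is smaller whenever c > 0 and d > 0. If no record is dated after the cut-off, c = 0 throughout and the curves are identical.

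**Inputs from the documents.** Scans every 6 weeks (SAP 2.1.3.1); cut-off once all Part 2 patients have at least 4 postbaseline assessments (Protocol 6.2.2), taken as 4 × 6 = 24 weeks after the last entry; 29 patients at the selected dose (Protocol 11.1.1).

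**Assumptions not in the documents.** Exponential PFS; uniform accrual over 12 months; 15% of events are deaths without progression; 0, 3 or 6 months of post-cut-off data in the dataset. Progression is dated at the next scan. No patient has symptomatic deterioration, so any difference comes from the cut-off clause alone. 1000 runs per scenario.

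**Mean Kaplan-Meier PFS, Table 20 / Table 21 (%)**

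| True median (months) | Post-cut-off data (months) | 6-month | 9-month | 12-month | Runs in which the estimated median changed |
|---|---|---|---|---|---|
| 6 | 0 | 52.7 / 52.7 | 38.1 / 38.1 | 27.3 / 27.3 | 0.0% |
| 3 | 3 | 27.3 / 27.2 | 14.1 / 12.7 | 7.3 / 5.5 | 0.0% |
| 4 | 3 | 38.3 / 38.3 | 23.7 / 21.8 | 14.4 / 11.4 | 0.1% |
| 6 | 3 | 51.8 / 51.7 | 37.7 / 35.4 | 27.0 / 22.7 | 6.4% |
| 9 | 3 | 65.1 / 65.0 | 52.4 / 49.8 | 42.2 / 36.9 | 40.4% |
| 6 | 6 | 52.6 / 52.5 | 38.4 / 36.7 | 27.9 / 23.2 | 5.2% |

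With 3 months of post-cut-off data, the 12-month rate drops by 7.3 − 5.5 = 1.8, 14.4 − 11.4 = 3.0, 27.0 − 22.7 = 4.3 and 42.2 − 36.9 = 5.3 points at true medians of 3, 4, 6 and 9 months. At 6 months, about 6.5 of the 29 patients have their censoring time shortened and about 2.6 events fall after the cut-off.

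**Which median is plausible?** The nearest figure in the documents is 63% without progression at 12 weeks, in the first-in-human study at 90 mg/m² D1D8 in mixed tumors (Protocol 4.1.2 and 4.2). If PFS is exponential, the median is 12 × ln 2 / (−ln 0.63) = 12 × 0.693 / 0.462 ≈ 18.0 weeks, about 4.1 months. A separate simulation with 3 months of post-cut-off data gave 12-month PFS of 15.3% against 11.9% at that median (3.4 points), and 28.0% against 23.3% at 6 months (4.7 points). With 1 to 3 months of such data the drop runs from about 1 to 5 points.

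**Symmetric rules.** Using all data to lock, and cutting both events and follow-up at the cut-off, give the same late PFS estimates. The downward shift comes from treating the two differently, not from having a cut-off.

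**The case against.** The strongest defence is that the clause may never act. Protocol 9.1.2 ends tumor assessments at progression or study cut-off, whichever is first. SAP section 4 plans database lock on essentially the condition that defines the second cut-off. If the data are cut there, no last assessment can fall after the cut-off, and Tables 20 and 21 give the same result. The SAP describes no later PFS update.

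A further defence is that a row naming a cut-off most naturally assumes that event status is also fixed at that date. The event rows are silent; they do not instruct anyone to count later events. The effect is also modest: at a median of about 4 months the 12-month gap is about 3 points, against a between-trial standard deviation of about 7 points for the estimate itself.

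Most of this stands, so a reader who infers that the sensitivity analysis is certainly biased goes further than the documents allow. Three things survive. SAP section 4 says when the lock occurs; it does not exclude records dated after the cut-off. Protocol 6.2.2 and 10.1.7 do plan such records. And if the clause never acts it is redundant, yet it still contradicts 2.1.3.2.4. The standard deviation does not remove the point either, because both curves come from the same patients and the gap between them is systematic.

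**Conclusion.** The inconsistency is established from the text: one stated rule for both PFS analyses, one table that follows it, and one that adds an undefined cut-off to its censored row only.

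The numerical consequence is conditional. It needs both post-cut-off data in the dataset and a literal reading of Table 21. Then the sensitivity curve sits below the primary curve at 9 and 12 months, by about 1 to 5 points at 12 months for assumed medians of 3 to 6 months and 1 to 3 months of post-cut-off data. The 6-month rate moves by about 0.1 point at most. The estimated median is essentially untouched at true medians up to 4 months and changes often only near 9 months. These sizes rest on assumed accrual, PFS distribution and data lag. Without post-cut-off data the difference is zero.

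A reader might also infer a threat to the trial's conclusions. The documents do not support that: PFS is secondary and descriptive, and dose selection and the rule of 7 responses in 29 patients rest on ORR (with safety for dose selection). This is a minor point, worth correcting because the correction costs almost nothing.

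**What to change.** Make the censored row of Table 21 identical to that of Table 20 and consistent with SAP 2.1.3.2.4, that is, "Date of last valid tumor assessment without evidence of progression", by deleting the reference to the earlier of two dates and to the cut-off. The two analyses then differ only in whether symptomatic deterioration counts as an event.

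If a data cut is intended, state it once in 2.1.3.2.4: name which of the two cut-offs in Protocol 6.2.2 applies, and limit events and censoring alike to data up to that date in both PFS analyses. This should be a deliberate choice, because a cut at the second cut-off would leave out of PFS the imaging that the protocol collects for 6 months afterwards.

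The cost is one table cell, or one sentence and one cell. No new data or analyses are needed.
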